2.7 Analysis of other variables

MEDu and MEDp collected from study subjects are used to derive SPF. MEDu and MEDp themselves will not be summarised or analysed. However, a listing for all MED determinations will be provided including the provisional determination (at Visit 3) of the unprotected skin and the final determination (at Visit 5) of both protected and unprotected skin (Listing 16.2.6).

Document Name	16.1.7 Documentation of statistical methods.pdf		
Туре	Version	Document Identifier	Effective Date
eldo clinical doc	1.0; CURRENT; Most-Recent; Effective	090032d580dcf91b	(8-Dec-2017 11:01:02
Reason For Issue	Imported as Effective from Legacy System		

GSK Consumer Healthcare Confidential Page 12
Statistical Analysis Plan Forte/207640

2.8 Interim analysis

There is no formal interim analysis. The procedure described in sample size determination will be performed by site staff.

2.9 Sample size calculation

Healthy volunteers aged between 18-70 years (inclusive) with Fitzpatrick phototype I, II or III, an ITA° value greater than 28° and who are untanned on the test area will be recruited for this study. The study will contain a population of subjects of more than one Fitzpatrick phototype.

To complete the study successfully, the minimum number of valid individual sun protection factor (SPFi) results will be 10 and the maximum number of valid SPFi results will be 20 for both the test product and positive control. In order to achieve between 10 and 20 valid SPFi results, a maximum of 5 individual invalid results may be excluded from the calculation of the mean SPF. Consequently, the actual number of subjects used for the study will fall between a minimum of 10 and a maximum of 25 (i.e. a maximum of 20 valid SPFi results plus 5 rejected invalid results).

In order to determine the number of test subjects, the 95% confidence interval (95% CI) of the mean SPF shall be taken into account. A minimum of 10 subjects shall be tested. The test shall be considered valid for the first 10 subjects if the resulting range of the 95% CI of the mean SPF is within $\pm 17\%$ of the mean SPF. If it is not within $\pm 17\%$ of the mean SPF, the number of subjects shall be increased stepwise from the minimum number of 10 until the 95% CI statistical criterion is met (up to a maximum of 20 valid results from a maximum of 25 subjects tested). If the statistical criterion has not been met after 20 valid results from a maximum of 25 subjects, then the test shall be rejected.

3 Changes to the Protocol Defined Statistical Analysis Plan

There were no changes or deviations to the originally planned statistical analysis specified in the protocol version 1.0 [(Dated: 28/Mar/2017)].

Document Name	16.1.7 Documentation of statistical methods.pdf		
Туре	Version	Document Identifier	Effective Date
eldo clinical doc	1.0; CURRENT; Most-Recent; Effective	090032d580dcf91b	(8-Dec-2017 11:01:02
Reason For Issue	Imported as Effective from Legacy System		

GSK Consumer Healthcare Confidential Page 13
Statistical Analysis Plan Forte/207640

4 Appendix 1:

4.1 List of Tables, Listings and Figures

4.2 Tables

Table Number	Table Title (Population)	Template
14.1.1	Subject Disposition (All Screened Subjects)	Appendix 2
14.1.2.1	Subject Demographics and Baseline Characteristics	Appendix 2
	(Safety Population)	
14.1.2.2	Subject Demographics and Baseline Characteristics	14.1.2.1
	(Analysis Population)	
14.2.1.1	Summary of Sun Protection Factor by Treatment	Appendix 2
	(Analysis Population)	
14.3.1.1	Treatment Emergent Adverse Events (Safety	Appendix 2
	Population)	
14.3.1.2	Treatment Emergent Adverse Events by Severity	Appendix 2
	(Safety Population)	
14.3.1.3	Treatment Emergent Treatment Related Adverse	14.3.1.1
	Events (Safety Population)	
14.3.1.4	Treatment Emergent Treatment Related Adverse	14.3.1.2
	Events by Severity (Safety Population)	

4.3 Listings

Listing Number	Listing Title (Population)	Template
14.3.2.1	Listing of Deaths (Randomised population)	16.2.7.1
14.3.2.2	Listing of Serious Adverse Events leading to	16.2.7.1
	Discontinuation (Randomised population)	
16.1.7	Randomisation Information (Randomised	Appendix 2
	Population)	
16.2.1	Individual Subjects Protocol Violations	Appendix 2
	(Randomised Population)	
16.2.2	Protocol Violations Leading to Exclusion from	Appendix 2
	Analysis Population (Randomised Population)	
16.2.4.1	Demographic Characteristics	Appendix 2
	(Randomised Population)	
16.2.4.2	Prior and Concomitant Medications	Appendix 2
	(Randomised Population)	
16.2.4.3	Listing of the identification for Technician	Appendix 2
	(Randomised Population)	
16.2.6	Individual Subject Efficacy Data (Randomised	Appendix 2

Document Name	16.1.7 Documentation of statistical methods.pdf		
Туре	Version	Document Identifier	Effective Date
eldo clinical doc	1.0; CURRENT; Most-Recent; Effective	090032d580dcf91b	(8-Dec-2017 11:01:02
Reason For Issue	Imported as Effective from Legacy System		

GSK Consumer Healthcare Confidential Page 14
Statistical Analysis Plan Forte/207640

Listing Number	Listing Title (Population)	Template
	Population)	
16.2.7.1	All Adverse Events (Randomised Population)	Appendix 2
16.2.7.2	All Adverse Events (Non-Randomised Subjects)	16.2.7.1

Note: If there are no data to display generate a null listing.

4.4 Top line Outputs:

Table/Listing	Table/Listing/Figure Title (Population)	
Figure Number		
14.1.1	Subject Disposition (All Screened Subjects)	
14.1.2.1	Subject Demographics and Baseline Characteristics (Safety Population)	
14.2.1.1	Summary of Sun Protection Factor by Treatment (Analysis Population)	
14.3.1.1	Treatment Emergent Adverse Events (Safety Population)	
16.2.7.1	All Adverse Events (Randomised Population)	

Document Name	16.1.7 Documentation of statistical methods.pdf		
Туре	Version Document Identifier Effective Date		
eldo_clinical_doc	1.0; CURRENT; Most-Recent; Effective 090032d580dcf91b (8-Dec-2017 11:		(8-Dec-2017 11:01:02
Reason For Issue	Imported as Effective from Legacy System		

Confidential

Page 15 Forte/207640

5 Appendix 2:

5.1 Templates for the Tables, Listings and Figures

This is a guideline which will give the guidance of treatment labels that will be used for the table header and in the figures, listings and in the footnotes.

The treatment labels for the column headings will be as follows:

- Physiogel Daily Defence
- P3 Standard

Document Name	16.1.7 Documentation of statistical methods.pdf		
Туре	Version Document Identifier Effective Date		
eldo_clinical_doc	1.0; CURRENT; Most-Recent; Effective 090032d580dcf91b (8-Dec-2017		(8-Dec-2017 11:01:02
Reason For Issue	Imported as Effective from Legacy System		

Confidential

Page 16 Forte/207640

Protocol: 207640

Page x of y Program Run Date:ddmonyyyy

Table 14.1.1 Subject Disposition All Screened Subjects

A ll Screened Subjects (N=XX)	
	Overall(N=XX)
	n (%)
TOTAL NUMBER OF SUBJECTS SCREENED	xx
SUBJECTS NOT RANDOMISED	Xx (xx.x)
DID NOT MEET STUDY CRITERIA	xx (xx.x)
ADVERSE EVENTS	xx (xx.x)
LOST TO FOLLOW UP	xx (xx.x)
PROTOCOL DEVIATION	xx (xx.x)
WITHDRAWAL OF CONSENT	xx (xx.x)
OTHER	xx (xx.x)
SUBJECTS RANDOMISED	xx (xx.x)
COMPLETED	xx (xx.x)
DID NOT COMPLETE	xx (xx.x)
DID NOT MEET STUDY CRITERIA	
ADVERSE EVENT	xx (xx.x)
LOST TO FOLLOW UP	xx (xx.x)
PROTOCOL DEVIATION	xx (xx.x)
WITHDRAWAL OF CONSENT	xx (xx.x)
OTHER	xx (xx.x)

Document Name	16.1.7 Documentation of statistical methods.pdf		
Туре	Version Document Identifier Effective Date		
eldo_clinical_doc	1.0; CURRENT; Most-Recent; Effective 090032d580dcf91b (8-Dec-2017 11:01:		(8-Dec-2017 11:01:02
Reason For Issue	Imported as Effective from Legacy System		

Confidential Page 17

Forte/207640

	Overall(N=XX)
	n (%)
DOMISED POPULATION	xx (xx.x)
TY POPULATION	xx (xx.x)
LYSIS POPULATION	xx (xx.x)

Program: PPD Source: PPD

For Non-Randomised section percentages has been calculated based on total number of subjects screened. For Randomised section percentages has been calculated based on total number of subjects randomised.

Note to programmer: For subjects not randomised and subjects not completing the study, the reasons should be consistent with the reasons in eCRF.

Document Name	16.1.7 Documentation of statistical methods.pdf			
Туре	Version Document Identifier Effective Date			
eldo_clinical_doc	1.0; CURRENT; Most-Recent; Effective 090032d580dcf91b (8-Dec-2017 11:0		(8-Dec-2017 11:01:02	
Reason For Issue	Imported as Effective from Legacy System			

Confidential

Forte/207640

Page 18

Protocol: 207640

Page x of y Program Run Date:ddmonyyyy

Table 14.1.2.1 Subject Demographics and Baseline Characteristics Safety Population

Safety Population (N=XX)	
	Overall Overall
	(N=XX)
SEX n (%)	
MALE	xx (xx.x)
FEMALE	xx (xx.x)
RACE n (%)	
ASIAN - CENTRAL/SOUTH ASIAN HERITAGE	xx (xx.x)
AFRICAN AMERICAN/AFRICAN HERITAGE	xx (xx.x)
AMERICAN INDIAN OR ALASKAN NATIVE	xx (xx.x)
NATIVE HAWAIIAN OR OTHER PACIFIC ISLANDER	xx (xx.x)
WHITE - WHITE/CAUCASIAN/EUROPEAN HERITAGE	xx (xx.x)
(include all captured as in eCRF)	xx (xx.x)
AGE (YEARS)	
n	XX
MEAN	XX.X
SD	XX.XX
MEDIAN	XX.X
MINIMUM	XX

Document Name	6.1.7 Documentation of statistical methods.pdf		
Туре	Version Document Identifier Effective Date		
eldo_clinical_doc	1.0; CURRENT; Most-Recent; Effective 090032d580dcf91b (8-Dec-2017 11:01:02		
Reason For Issue	Imported as Effective from Legacy System		
Confidential	Page 1	9	

Forte/207640

	Overall Overall
	(N=XX)
MAXIMUM	XX
TEXTION	
ITAº	VV
n	XX
MEAN	XX.X
SD	XX.XX
	XX.X
MEDIAN	XX
MINIMUM	
MAXIMUM	XX
FITZPATRICK SCALE FOR SKIN TYPE	
I = ALWAYS BURNS EASILY: NEVER TANS	xx (xx.x)
II = ALWAYS BURNS EASILY: TANS MINIMALLY	xx (xx.x)
III = BURNS MODERATELY: TANS GRADUALLY	xx (xx.x)
IV = BURNS MINIMALLY: ALWAYS TANS WELL	xx (xx.x)
V = RARELY BURNS: TANS PROFUSELY	xx (xx.x)
VI = NEVER BURNS: DEEPLY PIGMENTED	xx (xx.x)

Program: PPD Source: PPD

Programming Note: The similar descriptive statistics should be provided for meanL* and meanb*.

Document Name	16.1.7 Documentation of statistical methods.pdf		
Туре	Version Document Identifier Effective Date		
eldo_clinical_doc	1.0; CURRENT; Most-Recent; Effective 090032d580dcf91b (8-Dec-2017 11		(8-Dec-2017 11:01:02
Reason For Issue	Imported as Effective from Legacy System		

Confidential

Page 20 Forte/207640

Protocol: 207640

Page x of y
Program Run Date:ddmonyyyy

Table 14.2.1.1 Summary of Sun Protection Factor by Treatment Analysis Population

A nalysis	Population	(N=XX)
	-	

Visit	Variable	Physiogel Daily Defence	P3 Standard
		(N=XX)	(N=XX)
VISIT 5	n (number of invalid cases)	xx	XX
		Summary for Valid Case	s
	n (number of valid cases)	xx	xx
	MEAN	x.xx	x.xx
	SD	x.xxx	x.xxx
	95% CI	(x.xx, x.xx)	(x.xx, x.xx)
	CI[%]	XX.X	xx.x

Program: PPD Source: PPD

Note to programmer: 1. Keep two decimal places for mean, 95% CI.

2. Keep three decimal places for SD.

Document Name	16.1.7 Documentation of statistical methods.pdf						
Туре	Version	Document Identifier	Effective Date				
eldo_clinical_doc	1.0; CURRENT; Most-Recent; Effective	090032d580dcf91b	(8-Dec-2017 11:01:02				
Reason For Issue	Imported as Effective from Legacy System						

Confidential

Page 21 Forte/207640

Protocol: 207640

Page x of y Program Run Date:ddmonyyyy

Table 14.3.1.1
Summary of Treatment Emergent Adverse Events
Safety Population

Safety Population (N=xx)		Sureey 1 opt	414(10)			
System Organ Class and Preferred Term	Physiogel Daily Defence (N=XX)		P3 Standard	Overall (N=XX)		
			(N=XX)			
-	n (%)	nAE		n (%)	nAE	
NUMBER OF SUBJECTS WITH AT LEAST ONE AE	xx (xx.x)	xx	•••	xx (xx.x)	xx	
NUMBER OF SUBJECTS WITH NO AE	xx (xx.x)	XX		xx (xx.x)	xx	
SKIN AND SUBCUTANEOUS TISSUE DISORDERS	xx (xx.x)	xx		xx (xx.x)	xx	
ERYTHEMA	xx (xx.x)	xx	•••	xx (xx.x)	XX	
DERMATITIS	xx (xx.x)	XX	•••	xx (xx.x)	xx	
GASTROINTESTINAL SYSTEM	xx (xx.x)	XX	•••	xx (xx.x)	xx	
ABDOMINAL PAIN	xx (xx.x)	xx	•••	xx (xx.x)	xx	
DRY MOUTH	xx (xx.x)	xx	•••	xx (xx.x)	XX	
VOMITING	xx (xx.x)	xx		xx (xx.x)	XX	

n (%) = Number (percent) of subjects; nAE = Number of adverse events.

Program: PPD Source: PPD

Document Name	cument Name 16.1.7 Documentation of statistical methods.pdf						
Туре	Version	Document Identifier	Effective Date				
eldo_clinical_doc	1.0; CURRENT; Most-Recent; Effective	090032d580dcf91b	8-Dec-2017 11:01:02				
Reason For Issue	Imported as Effective from Legacy System						

Confidential

Page 22 Forte/207640

Safety Population (N=xx)

Protocol: 207640

Page x of y
Program Run Date:ddmonyyyy

Table 14.3.1.2 Summary of Treatment Emergent Adverse Events by Severity Safety Population

System Organ Class and Preferred Term		Р	hysiogel Dai	ly Defen	ice		P3 Standard				Overall		
			(N=X)	()			(N=XX)				(N=XX)		
	Mild		Moderat	te	Seve	re		Milo	d	Moder	rate	Seve	re
	n (%)	nAE	n (%)	nAE	n (%)	nAE		n (%)	nAE	n (%)	nAE	n (%)	nAE
NUMBER OF SUBJECTS WITH AT LEAST ONE AE	xx (xx.x)	XX	xx (xx.x)	xx	xx (xx.x)	xx	•••	xx (xx.x)	xx	xx (xx.x)	xx	xx (xx.x)	xx
		XX		XX		XX	• • •		XX		XX		XX
SKIN AND SUBCUTANEOUS TISSUE DISORDERS	xx (xx.x)	xx	xx (xx.x)	xx	xx (xx.x)	xx		xx (xx.x)	xx	xx (xx.x)	xx	xx (xx.x)	xx
ERYTHEMA	xx (xx.x)	XX	xx (xx.x)	XX	xx (xx.x)	XX	•••	xx (xx.x)	XX	xx (xx.x)	XX	xx (xx.x)	XX
DERMATITIS	xx (xx.x)	xx	xx (xx.x)	xx	xx (xx.x)	xx	•••	xx (xx.x)	XX	(xx.x)	xx	xx (xx.x)	xx
GASTROINTESTINAL SYSTEM	xx (xx.x)	xx	xx (xx.x)	xx	xx (xx.x)	xx	•••	xx (xx.x)	xx	xx (xx.x)	xx	xx (xx.x)	xx
ABDOMINAL PAIN	xx (xx.x)	xx	xx (xx.x)	xx	xx (xx.x)	xx	•••	xx (xx.x)	xx	xx (xx.x)	xx	xx (xx.x)	xx
DRY MOUTH	xx (xx.x)	xx	xx (xx.x)	XX	xx (xx.x)	XX	•••	xx (xx.x)	XX	xx (xx.x)	xx	xx (xx.x)	xx
VOMITING	xx (xx.x)	XX	xx (xx.x)	XX	xx (xx.x)	xx	•••	xx (xx.x)	xx	`xx ((xx.x)	xx	xx (xx.x)	xx

n (%) = Number (percent) of subjects; nAE = Number of adverse events.

Program: PPD Source: PPD

Document Name	16.1.7 Documentation of statistical methods.pdf							
Туре	Version	Document Identifier	Effective Date					
eldo_clinical_doc	1.0; CURRENT; Most-Recent; Effective	090032d580dcf91b	8-Dec-2017 11:01:02					
Reason For Issue	Imported as Effective from Legacy System							

Confidential

Forte/207640

Page 23

Protocol: 207640

Page x of y Program Run Date:ddmonyyyy

Listing 16.1.7
Randomisation Information
Randomised Population

Subject	Age/Sex/Race[1]	Randomisation Number	Test Site/Treatment	Date of randomisation (dd/mmm/yyyy)
Number			Randomised	
PPD				PPD

[1] Age in years; Sex: F = Female, M = Male; Race: A = Asian, B = Black or African American, I = American Indian or Alaska Native, H = Native Hawaiian or Other Pacific Islander, W = White, O = Multiple.

Program: PPD Source: PPD

Note to programmer: Check actual races captured in eCRF to adjust the race name and abbreviations

Document Name	16.1.7 Documentation of statistical methods.pdf						
Туре	Version	Document Identifier	Effective Date				
eldo_clinical_doc	1.0; CURRENT; Most-Recent; Effective	090032d580dcf91b	(8-Dec-2017 11:01:02				
Reason For Issue	Imported as Effective from Legacy System						

Confidential Page 24

Forte/207640

Protocol: 207640

Page x of y Program Run Date:ddmonyyyy

Listing 16.2.1 Individual Subjects Protocol Violations Randomised Population

Subject Number	Age/Sex/Race[1]	Visit	Deviation Sequence	Protocol Deviation
PPD		3	1	xxxxxxxxxxxxxxxxxxxxxxxxxxxxx

Program: PPD Source: PPD

Note to programmer: Check actual races captured in eCRF to adjust the race name and abbreviations

^[1] Age in years; Sex: F = Female, M = Male; Race: A = Asian, B = Black or African American, I = American Indian or Alaska Native, H = Native Hawaiian or Other Pacific Islander, W = White, O = Multiple.

Document Name	16.1.7 Documentation of statistical methods.pdf						
Туре	Version	Document Identifier	Effective Date				
eldo_clinical_doc	1.0; CURRENT; Most-Recent; Effective	090032d580dcf91b	(8-Dec-2017 11:01:02				
Reason For Issue	Imported as Effective from Legacy System						

Confidential

Page 25 Forte/207640

Protocol: 207640

Page x of y Program Run Date:ddmonyyyy

Listing 16.2.2

$\begin{array}{c} {\tt Protocol\ Violations\ Leading\ to\ Exclusion\ from\ Analysis\ Population} \\ {\tt Randomised\ Population} \end{array}$

Subject Number	Deviation Sequence	Start Date	End Date	Deviation Description
PPD	1	28MAR2017	28MAR2017	XXXXXXXX

Program: PPD Source: PPD

Document Name 16.1.7 Documentation of statistical methods.pdf						
Туре	Version	Document Identifier	Effective Date			
eldo_clinical_doc	1.0; CURRENT; Most-Recent; Effective	090032d580dcf91b	(8-Dec-2017 11:01:02			
Reason For Issue	Imported as Effective from Legacy System					

Confidential

Page 26 Forte/207640

Protocol: 207640

Page x of y Program Run Date:ddmonyyyy

Listing 16.2.4.1

Demographic Characteristics Randomised Population

Subject Number	Age	Sex	Race	MeanL*	Meanb [*]	ITA ⁰ Value	FITZPATRICK SCALE FOR SKIN TYPE
PPD				69.03	55.1	55.7	I = ALWAYS BURNS EASILY:
							NEVER TANS

••••••

Program: PPD Source: PPD

Document Name	16.1.7 Documentation of statistical methods.pdf		
Туре	Version	Document Identifier	Effective Date
eldo_clinical_doc	1.0; CURRENT; Most-Recent; Effective	090032d580dcf91b	(8-Dec-2017 11:01:02
Reason For Issue	Imported as Effective from Legacy System		
Confidential	Page 2	7	

Forte/207640

Protocol: 207640

Page x of y
Program Run Date:ddmonyyyy

Listing 16.2.4.2

Prior and Concomitant Medications Randomised Population

Subject Number	Screening Date	Medication	Dosage	Reason for Medication	Medication Start Date [1]	Medication End Date [1]	Ongoing Status Yes/No
PPD			10MG PO OD	HIGH BLOOD PRESSURE	2011	CONTINUING	YES

[1] Only known parts of partial dates are listed.

Program: PPD Source: PPD

Document Name	16.1.7 Documentation of statistical methods.pdf					
Туре	Version	Document Identifier	Effective Date			
eldo_clinical_doc	1.0; CURRENT; Most-Recent; Effective	090032d580dcf91b	(8-Dec-2017 11:01:02			
Reason For Issue	Imported as Effective from Legacy System					

Confidential

Forte/207640

Page 28

Protocol: 207640

Page x of y
Program Run Date:ddmonyyyy

Listing 16.2.4.3

Listing of the Identification for Technician Randomised Population

Subject Number	Irradiation at Visit 2	Visual Grading at Visit 3	Product Application and Irradiation at Visit 4	Visual Grading at Visit 5
PPD	AP	AP	AP	AP

Program: PPD Source: PPD

Programming Note: The AP is just an example, please use the real data while creating the listing.

Document Name	16.1.7 Documentation of statistical methods.pdf					
Туре	Version	Document Identifier	Effective Date			
eldo_clinical_doc	1.0; CURRENT; Most-Recent; Effective	090032d580dcf91b	(8-Dec-2017 11:01:02			
Reason For Issue	Imported as Effective from Legacy System					

Confidential

Forte/207640

Page 29

Protocol: 207640

Page x of y Program Run Date:ddmonyyyy

Listing 16.2.6 Individual Subjects Efficacy Data Randomised Population

Subject	Age/Sex/Race[1]	Visit	Test-	Sub-Site	Treatment	Variable	Variable Value	Valid /	Exclusion Justification
Number			Site					Excluded	
PPD						Provisional	x.xx		
						MEDu			
						MEDu	x.xx		
						MEDp test	x.xx		
						MEDp reference	x.xx		
						SPFi test	XX.X	Valid	
						SPFi reference	XX.X	excluded	invald fortest product
						Provisional	x.xx		
						MEDu			
						MEDu	x.xx		
						MEDp test	x.xx		
						MEDp reference	x.xx		
• • •						SPFi test	XX.X		
						SPFi reference	XX.X		

[1] Age in years; Sex: F = Female, M = Male; Race: A = Asian, B = Black or African American, I = American Indian or Alaska Native, H = Native Hawaiian or Other Pacific Islander, W = White, O = Multiple.

Program: PPD Source: PPD

Note to programmer: Check actual races captured in eCRF to adjust the race name and abbreviations.

Document Name	16.1.7 Documentation of statistical methods.pdf				
Туре	Version	Document Identifier	Effective Date		
eldo clinical doc	1.0; CURRENT; Most-Recent; Effective	090032d580dcf91b	8-Dec-2017 11:01:02		
Reason For Issue	Imported as Effective from Legacy System				

GSK Consumer Healthcare

Confidential

Forte/207640

Statistical Analysis Plan

Page 30

Protocol: 207640

Page x of v Program Run Date:ddmonyvyv

Source: PPD

Listing 16.2.7.1 All Adverse Events Randomised Population

Treatment Group: Physiogel Daily Defence/no treatment

Subject Number	Age/Sex/R ace[1]	Adverse Event (Preferred Term) (System Organ Class)	Start Date /Study Day[2]	Start Time	End Date	End Time	Frequency /Intensity [3]	Related to Study Product?	Action Taken re Study Product	Outcom e	Serious ?	Withdrew?[4]
PPD				PPD			Singl e/ MILD	No	NOT APPLICAB LE	RECOVE RED/RE SOLVED	NO	NO

[1] Age in years; Sex: F = Female, M = Male; Race: A = Asian, B = Black or African American, I = American Indian or Alaska Native, H = Native Hawaiian or Other Pacific Islander, W = White, O = Multiple.

- [2] Study day is the day relative to start of treatment, day 1 being the day of first treatment.
- [3] INT = Intermittent and SGLE = Single.
- [4] Did subject withdraw from study as a result of this adverse event?

Program: PPD

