A suitable warm-up time of at least 10 minutes will be allowed for the UV solar simulator to stabilize before starting exposures. This is to ensure a consistent irradiance over the whole exposure period. Irradiation procedures will be conducted with the subject lying horizontally on their front and in a room with controlled temperature (22 ± 4 °C).

The minimum area of each exposure sub-site will be 0.5 cm^2 . The minimum distance between borders of each exposure sub-site (spots) will be at least 0.8 cm. The distance between any exposure sub-site and any edge of the test site will be at least 1 cm.

Exposure of the test site to UV radiation will start 15 to 30 minutes after the application of the test product. Exposure of the positive control site to UV radiation will start 15 to 30 minutes after application of the positive control. Exposure of the unprotected site to UV radiation may happen at any point after demarcation of the test sites and after the 10 minutes required for the solar simulator to warm up. Exposure of the unprotected site, positive control and test product sites will be conducted sequentially, in any order, on same subject on the same day.

For the unprotected site, the range of UV doses administered shall be selected using the subject's provisional MED_u. Six exposure sub-sites centered on the provisional MED_u shall be exposed with incremental UV doses using a geometric progression of 1.25. The dose of UV radiation administered to subjects will be chosen such that the provisional MED_u will be irradiated on the 4th of the 6 sub-sites.

For the test product and reference formulation protected sites, the UV doses administered shall be selected using the subject's expected MED_p, which is the multiple of the expected SPF of the study product and the provisional MED_u for the subject. A minimum of 6 sub-sites centered on the expected MED_p shall be exposed

 GlaxoSmithKline	Document Name	207640 Protocol.doc		
	Type	Version	Document Identifier	Effective Date
	eldo_controlled	2.0; Most-Recent; Effective; CURRENT	090032d580d3df08	11-May-2017 13:45:31
	Reason For Issue	Auto Issue		

with incremental UV doses using a geometric progression of 1.25. The dose of UV radiation administered to subjects will be chosen such that the expected MEDp will be irradiated on the 4th of the 6 sub-sites. After the UV exposure procedures are complete, reference and test product may be gently removed by wiping with a dry tissue.

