2.4 Analysis of Sun Protection Factor (SPF)

2.4.1 Primary efficacy endpoint

2.4.1.1 Primary endpoint definition

The primary analysis will be based on sun protection factor (SPF). Individual SPF for each subject (SPFi) is defined as the ratio of his/her minimal erythemal dose of protected skin (MEDp) over unprotected skin (MEDu), i.e., SPFi = MEDp / MEDu (keeping 1 decimal place for individual SPF). As each subject will have both test product and reference product applied on two sites of dorsum together with an unprotected site, each subject will provide two individual SPFs, one for the test product, one for the reference product. The MEDp at two protected sites and MEDu at the unprotected site of each subject determined by a trained grader at Visit 5 will be used in primary analysis.

Summary statistics for SPF, including mean, standard deviation, will be presented by treatment. The 95% CIs for the mean SPFs of the two treatments will be constructed via t-statistic and presented together with summary statistics (Table 14.2.1.1. for Analysis Population). The study will be considered valid if

- the range of the 95% CI of the mean SPF is within ±17% of the mean SPF for each product;
- The mean SPF of the reference sunscreen formulation (P3) used in the test shall fall within the defined acceptance limits (lower limit, SPF 13.7; upper limit, 17.7).

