2.6 Safety

2.6.1.1 Adverse events and Serious Adverse Events

All adverse events (AEs) will be summarised by primary system organ class and preferred term

Treatment emergent adverse events (TEAEs), defined as the AEs reported after study product application, will be summarized by the number and percentage of subjects having any adverse event, any adverse event in each System Organ Class, and and the number of occurrences of each individual adverse event (Table 14.3.1.1). All TEAEs will also be tabulated by severity (Table 14.3.1.2). Treatment emergent AEs suspected of a relationship to study medication will be presented in a similar manner (Table 14.3.1.3). For treatment related AEs, these will also be presented by severity (Table 14.3.1.4).

Deaths occurring during treatment (if any) will be listed (Listing 14.3.2.1) by treatment, including the date and study day of death, and the principal cause of death. Non-fatal serious adverse events causing study treatment discontinuation will be listed (Listing 14.3.2.2).

AEs will be collected from the start of provisional MEDu irradiation procedure until 5 days after the last administration of the study product. SAEs however, if assessed as related to study participation or related to a GSK concomitant medication will be recorded from the time a subject consents to participate in the study up to and including any follow-up contact. All AEs will be listed in Listing 16.2.7.1 for randomised subjects and Listing 16.2.7.2 for non-randomised subjects.

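### Adverse event tables and the death listing are split by product although each subject receives both products at one visit, and no rule says how an event is assigned to one of them

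*SAP*

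**What the plan says.** **Design.** SAP 2.4.1.1 states: "As each subject will have both test product and reference product applied on two sites of dorsum together with an unprotected site". Protocol 6.4.4 adds: "Exposure of the unprotected site, positive control and test product sites will be conducted sequentially, in any order, on same subject on the same day". Randomisation (Protocol 5.8) allocates positions on the back within a subject. There are no parallel treatment groups.

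**Safety text.** SAP 2.6.1.1 gives treatment-emergent events as "defined as the AEs reported after study product application", without saying which product. It continues: "Treatment emergent AEs suspected of a relationship to study medication will be presented in a similar manner (Table 14.3.1.3"). For deaths: "Deaths occurring during treatment (if any) will be listed (Listing 14.3.2.1) by treatment". Protocol 7.3 asks the investigator to judge causality against study product and does not require a product or site to be named. Protocol 9.3.3 plans only a by-subject listing of events.

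**Shells.** Table 14.3.1.1 has a column "Physiogel Daily Defence (N=XX"), a matching P3 column and an Overall column, each counting subjects with one or more events. Table 14.3.1.2 repeats this by severity, and SAP 4.2 makes these two shells the templates for the related-event tables 14.3.1.3 and 14.3.1.4. Under "The treatment labels for the column headings will be as follows", Appendix 2 gives two labels, one for Physiogel and one for P3. Listing 16.2.7.1 carries the header "Treatment Group: Physiogel Daily Defence/no treatment". SAP 4.3 makes that listing the template for Listings 14.3.2.1, 14.3.2.2 and 16.2.7.2.

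**The concern.** A column headed with one product and its own N invites the reader to take its counts as events under that product. In this design a non-local event, such as the vomiting or abdominal pain shown as example rows in the shell, occurs in a person who is carrying both products. It has no single column to go in. A death is in the same position.

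Local skin events could be assigned by site, but the plan does not say so, and the adverse event listing has no field from which to do it.

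General safety of the test product is a stated objective in both documents (under the primary heading in Protocol section 2, secondary in SAP 1.2). SAP 4.4 makes Table 14.3.1.1 and Listing 16.2.7.1 top-line outputs. At stake is whether the test-product column can be reproduced and read correctly.

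**Working it through.** The plan gives no figure to reproduce here. The check compares the design with the shells and then works through two small illustrations.

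**Step 1. Look for an attribution rule.**

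| Item | Where | Identifies one product? |
|---|---|---|
| Products per subject | SAP 2.4.1.1, Protocol 6.4.4 | No: both, on the same day |
| Start of treatment emergence | SAP 2.6.1.1 | No: any study product |
| Relatedness | Protocol 7.3; Listing 16.2.7.1 | No: one question on study product |
| Test site of the event | Listing 16.2.7.1 | No such column |
| Columns of the event tables | Tables 14.3.1.1 to 14.3.1.4 | Yes: Physiogel and P3, plus Overall |
| Death listing | SAP 2.6.1.1 | By treatment |

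The outputs need a product for each event, and none of the inputs supplies one.

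**Step 2. A non-local event.** Assume all 25 subjects, the cap in Protocol 4.5, received both products. All three columns then have N = 25. Assume 2 of them vomit after application. Each of the two can be entered in both product columns, in one, or in neither, so each column count can be 0, 1 or 2:

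- possible pairs of product counts: 3 × 3 = 9
- possible percentages per product column: 0/25 = 0%, 1/25 = 4%, 2/25 = 8%
- Overall: 2/25 = 8% in every case

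With 10 subjects, the minimum number tested, the product percentages are 0/10 = 0%, 1/10 = 10% and 2/10 = 20%, and Overall is 2/10 = 20%. The event counts are assumptions. The result is general: only Overall is determined.

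**Step 3. A local event.** Assume one of 25 subjects develops dermatitis at the P3 site only.

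| Rule | Physiogel | P3 | Overall |
|---|---|---|---|
| SAP definition applied literally to each column | 1/25 = 4% | 1/25 = 4% | 1/25 = 4% |
| Assigned by site | 0/25 = 0% | 1/25 = 4% | 1/25 = 4% |

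Read literally, the definition charges the test product with a reaction at the reference site, because that subject also received the test product.

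**Step 4. Sites without a column.** A local event at the unprotected site, or at the provisional MEDu site if reported after product application, has no product column. It fits only under Overall.

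**Step 5. The listing header.** It matches neither label defined in Appendix 2 and does not name P3. Listing 16.2.7.2 inherits it for non-randomised subjects, who have no assignment at all.

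**The case against.** The best defence is that the tables already hold the remedy. An Overall column is present, a non-local event can be placed there alone, and those subject-level counts are sound. Product columns also have a proper use: two topical products sit on separate sites, and the shell's first example class is skin disorders. Disposition and demographics are shelled with one Overall column, so the authors did recognise the within-subject design. SAP 2.4.1.2 plans no formal inference beyond the SPF confidence interval, so no between-product test on adverse events is intended. At most 25 people are randomised, UV-induced local erythema is not an adverse event (Protocol 7.1.1), and events may be few. Deaths appear in a listing, not as a rate.

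Most of this stands, and it limits the consequence. It does not remove the fault. The layout allows a sensible allocation but does not direct one, and the stated definition, applied literally, gives the duplicated counts of Step 3.

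On the header, a reader might infer that the SAP has invented a treatment arm or dropped P3 from safety reporting. The documents do not support that. The header sits in a mock shell and is probably a leftover label, an untreated control is part of the design, and P3 has its own column in the event tables. A reader might also infer that the safety summary as a whole is meaningless. It is not, because Overall is valid.

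**Conclusion.** Wrong as written, of minor consequence. The per-product counts of non-local events in Tables 14.3.1.1 to 14.3.1.4 are either duplicated or arbitrary, deaths cannot sensibly be listed by treatment, and local events cannot be traced to a product through the structure of Listing 16.2.7.1. The Overall column remains correct, and the primary SPF result does not depend on any of this.

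The conclusion rests on three assumptions:

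- Subjects receive both products as planned. The safety population requires only some application (SAP 2.1.3), and Protocol 5.2 allows discontinuation after a failed application mass when there is no room for a new site. A few subjects may therefore have received one product only, and the product denominators could differ slightly.
- No attribution rule exists outside these two documents. The CRF was not available and may already hold a site field.
- The site is not recoverable from the reported event term. If investigators write it into the term, some local events could be assigned by hand, but the plan does not require that.

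**What to change.** 1. In SAP 2.6.1.1 and Tables 14.3.1.1 to 14.3.1.4, report non-local adverse events, SAEs and deaths once per subject, under Overall only. Remove the by-treatment wording for deaths.
2. Keep product or site columns only for local skin events. Assign these from the recorded test site and the randomisation: test product, P3, unprotected and, where relevant, the provisional MEDu site. State the rule in SAP 2.6.1.1 and in a table footnote.
3. Add a test-site column to Listing 16.2.7.1. Listings 16.1.7 and 16.2.6 already show test site and treatment, so the structure exists.
4. Replace the Listing 16.2.7.1 header with one that fits the design, and check it in the three listings that inherit it, in particular the one for non-randomised subjects.

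The cost is SAP and shell rewording, plus a site field for local events if the CRF does not have one. No subjects, visits or procedures are added.
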